3.1 Statement of Design

This is a prospective, randomised controlled, assessor-blinded, feasibility study with participants allocated to one of two parallel groups in a 1:1 fashion using randomisation by minimisation. The operating surgeon will be aware of the type of operation performed. The nature of the intervention (metatarsal amputation using either a bone saw or a bone cutter) ensures that both the patient and the assessor can be blinded, so long as the assessor is not the operating surgeon. Patients who are undergoing toe amputation via spinal or local anaesthesia, will be provided with headphones to ensure they do not overhear what equipment is requested. Evaluation of the post-operative x-rays will be performed by a designated trial radiologist who will be blinded to the intervention. The statistical analysis will be blinded. The primary trial centre will be University Hospital Galway, Ireland, with other centres also evaluated for inclusion. Appropriate patients shall be recruited from both the out-patient and in-patient setting. The procedures may be classed as Emergent, Urgent or Elective.

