study(12). There have been no randomised controlled trials evaluating the impact of metatarsal transection method on outcomes after ray amputation, specifically whether a manual bone cutter or an electric/oscillating/pneumatic bone saw were used. We hypothesise that utilising a manual bone cutter is more subject to inter-user variability, as it depends on the physical strength of the operating surgeon; improperly applied forces are liable to fracture the remaining bone, leaving small comminuted fragments that may become necrotic and act as a nidus for further infection within the wound bed. Furthermore, using an oscillating microsaw has the advantage of providing a clean bony transection regardless of the physical strength of the operator, however it may cause more damage to the surrounding connective tissues and disturb microvascular periosteal supply, which could also lead to osteonecrosis. We propose a pilot randomised controlled trial to test the feasibility and to generate sufficient data to permit sample size calculation for a trial designed to evaluate the outcomes after ray amputation using either a bone cutter or a bone saw.

4. **Objectives:**

The principal research question for this trial is as follows:

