2.2 Secondary Objectives

1. To determine the effect of oscillating microsaw compared to bone cutters for toe amputation on rates of surgical reintervention at six months;
2. To determine the effect of oscillating microsaw compared to bone cutters for toe amputation on re-infection rates;
3. To determine the effect of oscillating microsaw compared to bone cutters for toe amputation on time to surgical wound healing;

4. To determine the effect of oscillating microsaw compared to bone cutters for toe amputation on wound-related hospital readmissions at six months;
5. To determine the effect of oscillating microsaw compared to bone cutters for toe amputation on ulcer healing;
6. To determine the effect of oscillating microsaw compared to bone cutters for toe amputation on ulcer recurrence;
7. To determine the effect of oscillating microsaw compared to bone cutters for toe amputation on osteomyelitis recurrence in the affected foot;
8. To determine the effect of oscillating microsaw compared to bone cutters for toe amputation on resection specimen margin culture positivity;
9. To determine the effect of oscillating microsaw compared to bone cutters for toe amputation on patient-reported post-operative pain, as measured by the Verbal Rating Scale (VRS)(13, 14);
10. To determine the effect of oscillating microsaw compared to bone cutters for toe amputation on patient-reported health-related quality of life (HR-QoL) at 6 weeks and 6 months post-operatively, as measured by the EQ-5D-5L tool(15)

3. Study Design and Endpoints:

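### Blinding of awake patients rests on headphones meant to hide the spoken equipment request, although one arm uses a powered saw; the two patient-rated secondary comparisons may be unblinded and nothing planned would show it

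*Combined protocol and SAP*

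**What the plan says.** Section 3.1 (Statement of Design) labels the trial a "prospective, randomised controlled, assessor-blinded, feasibility study". The same section goes further and states that the nature of the intervention "ensures that both the patient and the assessor can be blinded, so long as the assessor is not the operating surgeon". It then gives one measure for masking the patient. It applies to "Patients who are undergoing toe amputation via spinal or local anaesthesia", who "will be provided with headphones to ensure they do not overhear what equipment is requested".

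The background section, before the objectives, frames the comparison as "whether a manual bone cutter or an electric/oscillating/pneumatic bone saw were used".

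Two of the ten secondary objectives in Section 2.2 are rated by the patient. Item 9 is "patient-reported post-operative pain, as measured by the Verbal Rating Scale", with no time point. Item 10 is the EQ-5D-5L at 6 weeks and 6 months. The primary efficacy endpoint (Section 3.2.1) is surgical reintervention at twelve months.

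**The concern.** The stated aim of the headphones stops at the conversation in theatre. The difference between the arms continues into the bone cut, when a motor runs in one arm only. The plan does not say whether anything is played through the headphones, what type they are, or how long they stay on. An awake patient may therefore learn which tool was used after the request has been successfully hidden.

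Blinding the radiologist and the statistical analysis, as Section 3.1 also plans, cannot protect an outcome that the patient rates. If awake patients know their tool, the comparisons under objectives 9 and 10 may partly reflect expectation. The study also exists to prepare a larger trial. Whether awake patients can be kept blind is a practical question that the larger trial will face, and as written the pilot gives no evidence on it.

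**Working it through.** **Check of the text.** The plan gives no figure on this point, so there is nothing to reproduce. I compared what would be needed to support the claim of patient blinding with what the document contains.

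- *Masking of the request:* covered by the headphones (Section 3.1).
- *Masking of the bone cut:* not described. There is no mention of played sound, noise cancelling, running the saw out of use in the cutter arm, or screening the patient's view.
- *Who is exposed:* patients under spinal or local anaesthesia. Their share is not given, and anaesthesia type is not among the baseline items in Section 4.5.
- *Detection of unblinding:* none. The visit table after Section 6.4 has no guess question or blinding check, and no section provides for recording unblinding.
- *Analysis:* Section 8 does not separate awake from other patients.

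**What a guess question could show at this size.** Section 8 gives 20 patients per arm. The other inputs below (how many are awake, how many guess correctly) are my assumptions.

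Bang's index for one arm is (correct − incorrect)/n, where don't-know answers count in n only. With no don't-know answers and a proportion p correct, this is BI = 2p − 1, with SE = √(4p(1−p)/n).

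*At chance, p = 0.5, so BI = 0:*
- n = 20 awake: SE = √(1/20) = 0.22; 95% half-width 1.96 × √(1/20) ≈ 0.44.
- n = 10 awake: SE = √(1/10) = 0.32; 95% half-width ≈ 0.62.

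*With 80% correct, BI = 0.60:*

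| Correct / awake | SE | Approximate (Wald) 95% interval | Exact 95% interval |
|---|---|---|---|
| 16 / 20 | √(4×0.8×0.2/20) = 0.179 | 0.25 to 0.95 | 0.13 to 0.89 |
| 8 / 10 | √(4×0.8×0.2/10) = 0.253 | 0.10 to 1.10 (beyond the maximum of 1) | −0.11 to 0.95 |

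If every patient in an arm is awake, marked unblinding can be told from chance. If half are awake, the same 80% correct cannot, on the exact interval. The index is therefore descriptive here. An interval that includes zero is weak evidence that blinding worked, because with 10 awake per arm it would also include substantial unblinding.

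**What cannot be computed.** The size or direction of any bias in the pain scale or the EQ-5D-5L cannot be derived. The documents give no share of awake patients, no standard deviation and no expected difference.

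**The case against.** The strongest reply has four parts.

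1. *The trial calls itself assessor-blinded, and the main deliverables are not touched.* This stands as a limit on scope. The primary objective is data for a power calculation, and the primary efficacy endpoint is not patient-reported. A reader might infer that the primary comparison is compromised; the documents do not support that. But Section 3.1 also claims that the patient can be blinded and provides headphones for it, so the claim needs adequate support or softer wording.

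2. *Headphones that block speech may also dampen the saw.* They may. The request is the stated aim of the measure, not necessarily the limit of its effect. A reader might infer that awake patients will be unblinded. The text supports only that they may be, because the safeguard is under-described rather than absent.

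3. *Several natural assumptions have no source.* This is correct. A reader might suppose that most of these operations are done under spinal or local anaesthesia, but no share is given. Nor do the documents say that the cutter is silent, that vibration is felt under anaesthesia, or which tool patients would prefer. The background describes possible harms of both tools, so no direction of expectation is established. The EQ-5D-5L is also collected weeks to months after the operation.

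4. *A guess question cannot settle the matter in 40 patients.* It cannot prove blinding. It also misleads if patients under general anaesthesia are pooled with the awake, since their guesses dilute the index. Both limits are met by reporting descriptively among awake patients.

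**Conclusion.** The point holds in limited form. Section 3.1 asserts patient blinding more firmly than its one measure supports: the stated purpose covers the equipment request, while the arms differ by a powered against a manual tool during the cut. The consequence is confined to secondary objectives 9 and 10, and within them to the awake patients, who may number anywhere from 0 to 40. Any bias is possible rather than demonstrated, and its size and direction are unknown. No planned item would reveal it.

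The conclusion rests on one assumption outside the documents: that a powered saw can be recognised by some awake patients if nothing masks it. This is a worthwhile improvement to a feasibility study and does not threaten its main result.

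**What to change.** 1. In Section 3.1, have all awake patients in both arms wear headphones with continuous audio from before the instrument is requested until the bone cut is finished.
2. In the same section, replace the verb *ensures* with *aims to* for patient blinding, and bring the design label and the blinding statement into line.
3. Add anaesthesia type to the recorded data.
4. Ask patients once after surgery, around the 48-hour x-ray in Section 5, which tool they think was used: saw, cutter or don't know.
5. In Section 8, report the guesses and Bang's index with intervals, by arm among awake patients, as description only. Do not treat an interval that includes zero as proof of blinding.
6. Describe pain and EQ-5D-5L as possibly unblinded in awake patients, and interpret them alongside the guesses.

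**Cost.** The change needs protocol wording, one CRF question and one data field. The 48-hour x-ray is an imaging step and the scheduled clinical follow-up starts at 6 weeks, so someone must be assigned to ask the question. The index will be imprecise, audio will not mask any vibration that is felt, and the claim of patient blinding may have to be softened. The change should be made before recruitment, because guesses cannot be reliably recovered later.

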3.2 Endpoints

3.2.1 Primary Efficacy Endpoint

The primary efficacy endpoint will be the number of patients in each group who underwent surgical reintervention at twelve months post-operatively.

3.2.2 Primary Safety Endpoint

The primary safety endpoint is the rate of vascular-related post-operative complications in each group.

4. Study Participants:

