4.2 Exclusion Criteria

1. Patients with significant peripheral arterial disease, as defined by ABPI <0.4 or digital pressures of <50mmHg, not undergoing concurrent revascularisation;
2. Patients unfit for surgery;
3. Patients unable to provide informed consent.

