7.1 Potential adverse events related to intervention

The risk of any significant adverse event occurring is deemed unlikely. All reasonable measures to avoid these events will be undertaken. Any adverse events (as described below) that occur will be recorded and reported in any trial data:

1. Bleeding requiring takeback to theatre for haemostasis or requiring transfusion of >1 unit packed red cells with corresponding drop in Hb >1g/dl ;
2. Venous thrombo-embolism;
3. Myocardial infarction;
4. Adverse reaction to local anaesthetic;
5. Major ipsilateral amputation, either below-knee amputation or above-knee amputation

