7.2 Definition of an adverse event

Any untoward medical event related directly or indirectly to an intervention as a result of participation in the trial.

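### The primary safety endpoint and the adverse-event list do not target the local bone and soft-tissue harms that the protocol attributes to the two tools

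*Combined protocol and SAP*

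**What the plan says.** Section 3.2.2 reads: "The primary safety endpoint is the rate of vascular-related post-operative complications in each group". The protocol does not say which events are vascular-related, over what period they count, or how an event is attributed to the amputation.

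The background, before the objectives, gives the reasons for expecting the tools to differ. A cutter used with badly applied force may fracture the remaining bone, "leaving small comminuted fragments that may become necrotic and act as a nidus for further infection within the wound bed". Of the saw it says "it may cause more damage to the surrounding connective tissues and disturb microvascular periosteal supply, which could also lead to osteonecrosis".

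Section 7.1 introduces its list with "Any adverse events (as described below) that occur will be recorded and reported in any trial data". The five items are bleeding (return to theatre or transfusion), venous thrombo-embolism, myocardial infarction, reaction to local anaesthetic, and major ipsilateral amputation. Section 7.2 is wider: "Any untoward medical event related directly or indirectly to an intervention as a result of participation in the trial". Section 6.1 is wider still, since it has any post-operative complication or concern recorded, without definition or grading.

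Section 4.2 excludes "Patients with significant peripheral arterial disease, as defined by ABPI <0.4 or digital pressures of <50mmHg, not undergoing concurrent revascularisation". Patients with disease of that severity can therefore enter if they are revascularised at the same time.

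**The concern.** A safety endpoint should be able to pick up the harms that the investigators think may differ between arms. Here the rationale is about bone and soft tissue at the cut, while the designated endpoint is about vascular complications. A tool that caused more fragments, osteonecrosis or wound-edge necrosis might show no excess on the primary safety endpoint. It might also show none on the 7.1 list, unless the damage progressed to serious bleeding or major amputation. Events from a separate arterial operation, unrelated to the choice of tool, could meanwhile enter the count.

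This matters in a pilot because the primary objective (2.1) is to collect data for sizing a later trial, and the discussion (section 10) promises a provisional comparison of safety. A pilot is the place to try out the definitions and event rates that the full trial will use. As written, it would deliver a rate for an undefined category that is not the one in question.

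**Working it through.** **No plan figure to reproduce.** The protocol gives no safety event rate, effect size, alpha or power. The only number is 20 + 20 = 40 patients (section 8). The main check is therefore a comparison of texts.

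**1. Each hypothesised harm against the safety provisions**

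| Harm in the background | Tool | In 3.2.2 | In 7.1 | Elsewhere in the plan |
|---|---|---|---|---|
| Fracture of remaining bone, comminuted fragments | Cutter | Not named | Not listed | X-ray within 48 hours for fragments (section 5), blinded reading (3.1); used by no objective or endpoint |
| Infection arising from necrotic fragments | Cutter | Not named | Not listed | Secondary objectives 2, 7 and 8 |
| Connective-tissue damage | Saw | Not named | Not listed | Indirectly: objective 3 (wound healing), fortnightly photographs (6.1) |
| Periosteal disturbance, osteonecrosis | Saw | Not named; could be argued in or out | Not listed | 6-month x-ray for bony healing (6.1); named in no objective |

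None of the five items in 7.1 is one of these harms. None of the ten objectives in 2.2 names fragments, fracture, osteonecrosis or soft-tissue necrosis. Re-infection, osteomyelitis recurrence, healing and reintervention are compared, but they lie downstream of the injury.

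**2. What revascularisation events would do**

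Let p be the risk of a tool-related event and b a background risk of vascular or revascularisation events, equal in both arms and independent of p. The observed risk is 1 − (1 − p)(1 − b), so the difference between arms shrinks by the factor (1 − b). The documents give neither value. For illustration I assume p = 5% and 20%, and b from 0 to 30%. Sample sizes and power use the two-proportion formula (two-sided 5%, 80% power for n, no continuity correction).

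| b | Observed risks | Difference (points) | Risk ratio | n per arm | Power at 20 per arm |
|---|---|---|---|---|---|
| 0 | 5% v 20% | 15.0 | 4.0 | 76 | 29.5% |
| 10% | 14.5% v 28% | 13.5 | 1.93 | 143 | 17.6% |
| 20% | 24% v 36% | 12.0 | 1.50 | 228 | 12.7% |
| 30% | 33.5% v 44% | 10.5 | 1.31 | 337 | 9.9% |

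Example at b = 20%: 1 − 0.95 × 0.80 = 0.24 and 1 − 0.80 × 0.80 = 0.36, so the ratio is 0.36/0.24 = 1.5. The table is generous to the plan, because it assumes that the local harms are counted at all.

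**3. Bias or noise?**

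Allocation is 1:1 and randomised, so b is equal in expectation. Chance imbalance remains possible. If 20% to 40% of patients were revascularised (assumed), arms of 20 under simple randomisation would differ by four or more such patients with probability 16% to 26%. Pulse status is a stratification factor (4.1) and may reduce this.

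**4. Precision at 20 per arm**

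With 0 of 20 events the exact 95% upper limit is 1 − 0.025^(1/20) = 16.8%. With 4 of 20 the interval is 5.7% to 43.7%.

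**The case against.** The strongest reply is that much of the local harm is already observed. The secondary objectives compare the tools on re-infection, healing, osteomyelitis recurrence, margin culture and reintervention. X-rays are planned at 48 hours and 6 months with blinded reading, and 6.1 has any complication recorded. This stands, and it limits the point. It does not remove it, because the direct harms still belong to no endpoint, and recording without definitions may differ between sites.

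A second reply is that the study claims only a provisional comparison, and that 20 per arm cannot give a firm one whatever the endpoint. That is true, as the 16.8% upper limit shows. But the size of a pilot does not justify collecting the wrong event.

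A third is that, with the term undefined, ischaemic necrosis after disturbed periosteal supply might be counted as vascular-related, and that 3.2.2 is never tied to the 7.1 list. Both are correct, so exclusion of the saw's harm is not proven. The cutter's harm, fracture and fragments, does not fit the term on any ordinary reading.

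A fourth is that 7.1 and 7.2 limit adverse events to those related to an intervention through trial participation, so complications of a separate revascularisation need not count. That is a fair reading of section 7, but 3.2.2 carries no such limit. Section 4.5 records recent ipsilateral revascularisation, which helps, but it does not identify a concurrent procedure or attribute an event to it.

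**Conclusion.** The point holds as a mis-targeted safety endpoint, and not merely an undefined one. The harms that motivate the trial are absent from 3.2.2 and 7.1 and are covered elsewhere only in part. This conclusion rests on the text alone. The dilution figures (risk ratio 4.0 falling to between 1.93 and 1.31 for a background of 10% to 30%) rest on assumed rates and show direction and scale only.

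Three stronger readings are not supported:

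- A reader might infer that the trial cannot compare the tools' safety. The secondary objectives, blinded x-rays, open complication recording and wider definitions in 7.2 and 7.3 allow a partial comparison, and section 10 claims no more than a provisional one.
- A reader might infer that revascularisation biases the comparison. With randomised arms it adds noise and possible chance imbalance, not systematic error.
- A reader might infer that events such as "Major ipsilateral amputation, either below-knee amputation or above-knee amputation" are counted twice, as reintervention and as harm, and so overstate the evidence. Section 8 plans no analysis combining efficacy and safety, and 3.2.2 is not linked to the 7.1 list. Reporting such an event under both headings is not an error in itself.

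The change is worth making before recruitment, since the means of observing these harms are largely in place.

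**What to change.** Restate 3.2.2 as the proportion of patients in each group with a local complication of the index amputation site, meaning any of:

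- retained bony fragments or fracture of the residual metatarsal on the blinded 48-hour x-ray;
- osteonecrosis on the blinded 6-month x-ray;
- skin-edge or soft-tissue necrosis;
- bleeding at that site meeting item 1 of 7.1.

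State a time window for each component, matched to the planned x-rays and visits. Report the components separately as well as together, because a radiographic finding and a bleed do not carry the same weight.

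Add these events to 7.1, and reconcile its closed list with the open recording in 6.1 and the wider definition in 7.2.

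Keep vascular and systemic events as secondary safety outcomes. Record whether revascularisation was concurrent, and list these outcomes descriptively with and without those patients.

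The cost is endpoint wording and some data fields, filled from x-rays, fortnightly photographs and visits that are already planned. The downsides are slightly more event recording, a higher reported complication rate, and the need to agree a radiographic definition of osteonecrosis before the first film is read.

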4.1 Inclusion Criteria

Consenting patients, aged 18 and over, undergoing transmetatarsal amputation of one or more toes. Patients will be stratified by pulse status (at least one pedal palpable vs both pedal pulses impalpable) and chronic kidney disease (eGFR >60 and eGFR <60 mL/min/1.73m²), considering both are significant factors in predicting wound healing.

4.2 Exclusion Criteria

1. Patients with significant peripheral arterial disease, as defined by ABPI <0.4 or digital pressures of <50mmHg, not undergoing concurrent revascularisation;
2. Patients unfit for surgery;
3. Patients unable to provide informed consent.

